3.4 Follow-up and Analysis Time points

The follow-up schedule and analysis windows are listed below.

- Procedure (day 0)
- Discharge (discharge days = discharge date – implant date)
- 30-Day Visit \pm 7 Days [23, 37 days]
- 6-Month Follow-up (180 ± 30 days) [150, 210 days]
- 1 year Follow-up (365 ± 45 days) [320, 410 days]
- 2 years (730 days) \pm 45 days [685, 775 days]
- 3 years (1095 days) \pm 45 days [1055, 1140 days]

3.5 Missing Data Handling

All statistical analysis on the endpoints will be performed using only those patients with available data required for endpoint analysis. No missing value imputation will be performed.

No imputation will be done if the date variables are completely missing. For partial dates, only adverse event (AE) onset date will be imputed as follows:

- 1) If both month and day are missing
 - a. If the AE onset year is the same year as index procedure then use index procedure date to impute this AE onset date
 - b. Otherwise, assign January 1st for this AE onset date
- 2) If only day is missing
 - a. If the AE onset year and month are the same as the procedure ones then use the index procedure date to impute the AE onset date
 - b. Otherwise, assign '01' as the day for the AE onset date

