5.2.2 DEVICE SUCCESS ENDPOINT

Device Success will be assessed at 1 month, 6 months and annually and is defined as:

- Alive, with
- Original intended device in place, and
- No additional surgical or interventional procedures related to the device, and

- TR reduction (assessment made by change in EROA) compared to baseline and TV gradient ≤ 5 mmHg

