8.10 SUBJECT STUDY COMPLETION

Study subjects complete and exit the study when no additional follow-up visits, procedures, or data collection are required. Patients will then continue to be followed by their primary health care provider as required.

A subject will also be exited from the study in the following instances:

- Subject signs informed consent form, is deemed eligible and considered enrolled but does not undergo the study procedure
- Subject undergoes study procedure and does not receive investigational device (will continue in study for safety evaluations only and exit the study at the 6 month follow-up visit)
- Implanted subject requires the investigational device to be explanted for any reason (will continue in study for safety evaluations only and exit the study at the 6 month follow-up visit)
- Subject is lost-to-follow-up
- Subject withdraws participation from the study or is withdrawn from the study
- Subject expiration

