13.6 MISSING DATA

All possible steps will be taken to minimize missing data in the study, including monitoring of data forms for completeness and efforts to track and maintain contact with study subjects during the follow-up period.

All statistical analyses will be performed using available data. No missing value imputation will be performed.

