3.3 Additional Endpoint Analysis

Kaplan Meier estimates will be performed at the pre-specified follow-up times to project the estimates for time-related safety endpoints. The rate of freedom from all-cause mortality at 6 month, 1 year, 2 years, and 3 years will be estimated in addition to the primary endpoint which is established at 30 days post procedure.

Echocardiographic data will be analyzed by a core laboratory. The improvement from baseline for selected items will be presented as shift from baseline for each of the pre-specified follow-up periods. Subjects that are missing a baseline or follow-up values will be excluded from the analysis.

Subjects that undergo any type of repair or replacement procedure for the tricuspid valve will be excluded from the implant cohort analyses at the time of the re-intervention.

The average overall (general) quality of life at baseline, 1 month, 6 months and annually for 3 years and the changes from baseline to follow up will be summarized by mean and standard deviation for the implanted cohort. Patients that are missing a baseline or follow up values will be excluded from the analysis.

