4.3 Additional Endpoint Analysis

The following secondary endpoints and clinical outcomes will also be assessed

4.3.1 Technical Success (at exit from procedure room):

- Alive, with

- Successful access, delivery and removal of the delivery systems, and
- Deployment and correct positioning of the intended device, and
- No need for additional emergency surgery or re-intervention related to the device or access procedure

4.3.2 Device Success (at 1 month, 6 months & annually):

- Alive, with
- Original intended device in place, and
- No additional surgical or interventional procedures related to the device, and
- TR reduction (assessment made by change in EROA) compared to baseline and TV gradient $\leq 5\text{mmHg}$

4.3.3 Procedural Success (at 1 month):

- Device Success, and
- None of the following device or procedure related SAEs:
 - Life threatening bleeding
 - Major vascular or cardiac structural complications requiring intervention
 - Pericardial effusion requiring drainage or surgery (includes tamponade)
 - Stage 2 or 3 acute kidney injury (includes new dialysis).
 - Severe heart failure or hypotension requiring IV inotrope, ultrafiltration or mechanical circulatory support
 - Prolonged intubation > 48 hours

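### Device Success and Procedural Success: the re-intervention exclusion, and the available-data rule read literally, take known failures out of the denominator

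*SAP*

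**What the plan says.** **Endpoints.** Protocol 5.2.2 and SAP 4.3 define Device Success as an all-or-nothing composite, assessed at 1 month, 6 months and annually. The subject must be alive. The component list then has "Original intended device in place, and" after it the absence of further device-related procedures. The echo component is "TR reduction (assessment made by change in EROA) compared to baseline and TV gradient" of at most 5 mmHg. Procedural Success, assessed only at 1 month, requires Device Success plus "None of the following device or procedure related SAEs" (a list of six). Both are analysed in the implanted cohort (Protocol 13.3, SAP 2.4).

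**Missing data.** SAP 3.5 states: "All statistical analysis on the endpoints will be performed using only those patients with available data required for endpoint analysis". It continues: "No missing value imputation will be performed"; the only exception is partial adverse-event onset dates. Protocol 13.6 is similar: "All statistical analyses will be performed using available data. No missing value imputation will be performed".

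**Re-intervention.** SAP 3.3 and Protocol 13.5 exclude subjects with any tricuspid repair or replacement from the implanted-cohort analyses as of the re-intervention.

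**Explant.** Protocol 8.10 lists among the exit cases: "Implanted subject requires the investigational device to be explanted for any reason (will continue in study for safety evaluations only", with exit at the 6-month visit. Protocol Table 10 shows the safety evaluation and the transthoracic echocardiogram as separate rows, so no echo is scheduled for these subjects.

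Neither document says which data a composite requires once one component has failed, or that a known failure without an echo counts as a failure.

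**The concern.** For a mean change, leaving out a subject without a follow-up value is unavoidable unless the value is imputed. For these composites it is not. One failed component settles the outcome, so a subject who has died, lost the device or had a device-related procedure is classified without any echo.

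These are also the subjects for whom the plan's rules end echo follow-up or end inclusion in the cohort. Dropping them takes failures out of the denominator and never a success, so the bias can only be upward.

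Device performance is half of the stated objective, and Protocol section 2 says the data will be used to obtain regulatory approval. In a single-arm study no control group would expose an inflated success rate.

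**Working it through.** **Step 1. The plan's own figure.** Protocol 13.1 gives 63 subjects for at least 80% power at 0.05, with 30-day mortality of 7.5% against 18%. An exact one-sided binomial test at n = 63 rejects with 6 or fewer deaths, with alpha 0.0487 and power 0.808, so the figure reproduces. It sizes the primary endpoint only. Device Success and Procedural Success have no stated rate, goal or power. The 63 and the 7.5% serve below only as planning inputs.

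**Step 2. Each known failure against the rules.**

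| Event | Status by definition | What the rules do |
|---|---|---|
| Tricuspid repair or replacement that is device-related or removes the original device | Device Success failure | Expressly excluded (SAP 3.3, Protocol 13.5) |
| Explant | Device Success failure | No scheduled echo, exit at 6 months (8.10); dropped if SAP 3.5 is read literally |
| Death | Device Success failure | No echo possible; SAP 3.5 permits removal but does not clearly require it |
| Listed SAE by 1 month | Procedural Success failure | Survivors stay on the echo schedule; at risk only if the echo is missing |

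**Step 3. Size.** Let N be the number implanted, F the known failures dropped, and S the successes.

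- Rate with failures dropped: S/(N − F)
- Rate with failures counted: S/N
- Inflation factor: N/(N − F) = 1/(1 − F/N)

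Inputs: N = 63, taken as the implanted cohort (assumption). F = 5, because 63 × 0.075 = 4.7, as if 30-day deaths alone were dropped. Success among those with echo is assumed at about 50%, 70% or 90%. S is rounded to whole subjects.

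| F | Assumed success | Dropped | Counted | Overstatement (points) |
|---|---|---|---|---|
| 2 | 50% | 30/61 = 49.2% | 30/63 = 47.6% | 1.6 |
| 2 | 90% | 55/61 = 90.2% | 55/63 = 87.3% | 2.9 |
| 5 | 50% | 29/58 = 50.0% | 29/63 = 46.0% | 4.0 |
| 5 | 70% | 41/58 = 70.7% | 41/63 = 65.1% | 5.6 |
| 5 | 90% | 52/58 = 89.7% | 52/63 = 82.5% | 7.1 |
| 10 | 50% | 26/53 = 49.1% | 26/63 = 41.3% | 7.8 |
| 10 | 90% | 48/53 = 90.6% | 48/63 = 76.2% | 14.4 |

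At F = 5 the inflation factor is 63/58 = 1.086. In the 70% case the 95% Clopper-Pearson interval (the SAP 3.1 method) moves from 57.3–81.9% to 52.0–76.7%.

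**Step 4. Later visits, Device Success only.** F accumulates over three years. If cumulative dropped failures reached 20% or 30% (assumed), a reported 70% would correspond to 0.70 × 0.80 = 56% or 0.70 × 0.70 = 49%.

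**The case against.** The strongest reply is that SAP 3.5 can be read sensibly. It speaks of data required for the endpoint and never says an echo is required once another component has failed. For a dead or explanted subject, vital status or device status is available and decides the outcome. If every death left the denominator, the survival component could never fail. On that reading the bias from deaths and explants is zero. This stands as a fair reading, but the SAP does not state it, and it does not help with re-interventions, where the exclusion is explicit.

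A reader might infer more than the documents support:

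- **That the SAP orders deaths and listed SAEs to be removed.** It does not; the text is open on both.
- **That the SAP 3.3 sentence "Subjects that are missing a baseline or follow-up values will be excluded from the analysis" governs the composites.** It closes a paragraph on core-laboratory echo items shown as shifts from baseline, and nothing extends it further.
- **That subjects with a listed SAE tend to lack an echo.** Living implanted subjects stay on the full visit schedule, including echo (Protocol 8.7 and Table 10).
- **That the bias in Procedural Success grows over time.** It is assessed only at 1 month.

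The sizes are also illustrative. The 63 is the analysable number for the As Treated primary analysis, and the implanted cohort is a subset. The 7.5% is stated as an upper value, and As Treated deaths can include non-implanted subjects. The 5.6-point shift is small beside an interval about 25 points wide.

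The consequence is limited as well. These endpoints are secondary and carry no hypothesis. All-cause mortality is reported separately by Kaplan-Meier to 3 years, and deaths and adverse events are listed for all enrolled subjects, so deaths cannot be hidden.

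**Conclusion.** The point holds with graded strength. For tricuspid re-intervention, the plan expressly removes subjects whom its own definition makes failures whenever the procedure is device-related or the original device is lost. For explants, a literal reading of SAP 3.5 with Protocol 8.10 does the same. For deaths and listed SAEs it is an ambiguity that allows two denominators, one of them more favourable, with the choice left open until results are known.

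The direction is always upward. With 5 of 63 dropped the overstatement is 4.0 to 7.1 points for assumed success of 50–90%; with 2 to 10 dropped it is 1.6 to 14.4 points. The success rates, the number dropped and the later accumulation are assumptions; only 63 and 7.5% come from the plan. If few failures are dropped, for example re-interventions alone, the lower end applies.

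A reader might take this as a threat to the trial's main conclusion. It is not: 30-day mortality by Kaplan-Meier in the As Treated cohort needs no echo and is unchanged. The point is worth settling before analysis, but it is not critical.

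**What to change.** 1. **SAP 3.5 and 4.3, Device Success.** State that an implanted subject with a known failed component by the visit (death, original device not in place, device-related procedure) stays in the denominator as a failure at that and all later visits, with or without an echo.
2. **SAP 3.5 and 4.3, Procedural Success.** State that any such failure, or a listed SAE, by 1 month is a failure.
3. **SAP 3.3 and Protocol 13.5.** Confine the re-intervention exclusion to change-from-baseline summaries. Without this, the new rule and the exclusion would contradict each other.
4. **Unknowns.** Treat as unknown only subjects with no failed component and no evaluable echo. With S successes, K known failures and U unknowns, report S/(S + K) with the bounds S/(S + K + U) and (S + U)/(S + K + U).

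The cost is SAP wording, a matching change to Protocol 13.5 and one extra table row. Reported success will be slightly less favourable. No new data, imputation or change in sample size is needed, and the primary endpoint is untouched.

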3.6 Analysis Software

4. VARIABLE LIST FOR TABLE SHELLS

The following parameters will be summarized. Other parameters may be added as deemed necessary.

4.1 Demographics, Subject Characteristics, and Procedure Assessments

4.1.1 Demographics and Clinical Evaluation

- Age (in years)
- Gender
- Race/Ethnicity
- Body Mass Index (BMI)
- NYHA Class

4.1.2 Medical History

- Arrhythmia
- Cancer
- Carotid artery stenosis
- Coagulopathy
- Coronary artery disease
- Diabetes
- Hyperlipidemia
- Hypertension
- Liver Disease
- Myocardial infarction
- Pacemaker/ICD
- Peripheral vascular disease
- Prior Percutaneous Coronary Intervention
- Prior CABG
- Prior Valve Implant
- Pulmonary Disease
- Pulmonary Hypertension
- Stroke

- TIA

4.1.3 Procedure Information

- Time from Skin Incision to Closure Time (min)
- Time from Sheath Insertion to Device Lock (min)
- Fluoroscopy Time (min)
- Volume of Contrast Used (ml)

Implant Access Approach

- Left subclavian/axillary vein
- Right subclavian/axillary vein

- Spacer Size
 - 12mm
 - 15mm
 - 18mm
- Device permanently implanted
- Device implanted as intended
- Reintervention Required
- Device Malfunction

4.1.3 Implant Hospitalization Length of Stay (in days)

Days from index procedure to discharge of index procedure.

4.2 Primary Endpoint Analysis

- All-cause mortality at 30 days post-implant procedure

4.3 Additional Endpoint Analysis

The following secondary endpoints and clinical outcomes will also be assessed

4.3.1 Technical Success (at exit from procedure room):

- Alive, with

- Successful access, delivery and removal of the delivery systems, and
- Deployment and correct positioning of the intended device, and
- No need for additional emergency surgery or re-intervention related to the device or access procedure

4.3.2 Device Success (at 1 month, 6 months & annually):

- Alive, with
- Original intended device in place, and
- No additional surgical or interventional procedures related to the device, and
- TR reduction (assessment made by change in EROA) compared to baseline and TV gradient $\leq 5\text{mmHg}$

4.3.3 Procedural Success (at 1 month):

- Device Success, and
- None of the following device or procedure related SAEs:
 - Life threatening bleeding
 - Major vascular or cardiac structural complications requiring intervention
 - Pericardial effusion requiring drainage or surgery (includes tamponade)
 - Stage 2 or 3 acute kidney injury (includes new dialysis).
 - Severe heart failure or hypotension requiring IV inotrope, ultrafiltration or mechanical circulatory support
 - Prolonged intubation > 48 hours

4.3.4 Clinical Outcomes (at 1 month, 6 months & annually)

- Re-hospitalization rates for the underlying condition (heart failure)
- Re-intervention rates for the underlying condition (tricuspid regurgitation) Change in Tricuspid Regurgitation (assessment made by change in EROA) from baseline
- Change in peripheral edema as assessed by subject weight loss (kilograms) from baseline
- Change in NYHA Class from baseline
- Change in 6 minute walk test distance (meters) from baseline
- Change in Quality of Life as assessed by the SF-12 and KCCQ questionnaires from baseline

4.4 Transthoracic Echocardiogram (TTE) Parameters

- RA Area (cm²)
- RV End Diastolic Area (cm²)
- RV End Systolic Area (cm²)
- RA Volume (ml)
- RVED Volume (ml)
- RVES Volume (ml)
- RV EF (%)
- TAPSE (cm)
- RV Free Wall Thickness (cm)
- TV Annular Area 2D (cm²)
- TV Annular Area 3D (cm²)
- TV mean gradient (mmHg)
- LV EF (%)
- TR Vena Contracta inflow (cm)
- TR Vena Contracta Short Axis (cm)
- PISA EROA (cm²)
- Tricuspid Regurgitant volume (ml)
- Tricuspid Regurgitant EROA 2D (cm²)
- Tricuspid Regurgitant EROA 3D (cm²)
- Tricuspid Regurgitant RF (%)
- Jet Area (cm²)
- TR Jet VTI (cm)
- Tricuspid Leaflet Motion
- Tricuspid Leaflet Thickening
- Thrombus
- Pericardial Effusion
- Non-Study Valves AS
- Non-Study Valves AR
- Non-Study Valves MR
- Overall baseline TR

